6.6.3 Multiple imputation

For the analysis of the primary and key secondary endpoints, multiple imputation will be carried out, as specified in the protocol, using SAS PROC MI. Unless otherwise specified in the protocol, the seed 11109943 will be used.

When performing multiple imputation of continuous parameter values, imputed values at visits prior to Week 16 outside the relevant parameter scale shall be used as is. Values imputed at Week 16 shall be truncated to the nearest upper or lower bound on the given scale. For example, negative imputed EASI values at Week 16 will be set to 0.

For imputation of IGA values, the LIKELIHOOD=AUGMENT option will be used (1).

For imputation of IGA values, it may occur that the observed data from which the imputation model is fitted does not contain all levels of the IGA predictors necessary for the imputation. For example, the imputation model for IGA values at Week 8 will be based on observed data from the subset of subjects with observed IGA values at both Week 6 and Week 8. If only the IGA values (0,1,2,3) are observed at Week 6 in this subset of subjects, the imputation model will not be able to predict IGA values at Week 8 for a subject with an IGA value of 4 at Week 6. To avoid this situation, in this specific example IGA values of 3 and 4 at Week 6 will be combined into a single category for the purpose of the imputation. In general, if this situation arises, IGA categories will be combined into a single category at the specific visit for the purpose of the specific imputation, according to the rules in Table 1.

Table 1: Adjacent IGA categories combined in case of missing predictors in observed data

IGA value(s) missing in imputation model	IGA categories combined
0	(0,1)
1	(0,1)
2	(2,3)
3	(2,3)
4	(3,4)

Trial ID: LP0162-1343	Date: 15-Jun-2021	Version: 1.0 Page 12 of 22
-----------------------	-------------------	-------------------------------

6.6.4 Other endpoints and patient-reported outcomes:

The two binary other endpoints, reduction from baseline to Week 16 of DLQI ≥ 4 among subjects with baseline DLQI ≥ 4 and reduction from baseline to Week 16 of POEM score ≥ 4 points in subjects with baseline POEM score ≥ 4 , will be analysed as described for the primary analysis of the primary estimand ('composite') for the primary efficacy endpoints. In addition, the same endpoints will be evaluated at each scheduled visit/assessment up to Week 12.

Amount of TCS used

The amount of TCS used will be calculated as specified in section 6.6.6 and analysed in two ways, reflecting the two consumption assumptions. The primary analysis will be using the most conservative assumption that all missing tubes were fully used. The second assumption will be used as a sensitivity analysis, reflecting the primary analysis's extreme opposite, that all non-returned tubes were not used. The method used for analysis will be the one specified in the protocol. Additionally, descriptive histograms of both consumption assumptions will be produced.

Number of days without topical treatment use

The number of days without topical treatment use (collected as Patient Days of Topical Treatment Use in the eDiary) will be determined over 1-week periods from Week 0 until Week 16 and will be summarised over time by treatment group as specified in the protocol. Number of days without topical treatment use will be calculated using the same rules as for the Worst Daily Pruritus NRS (weekly average). In addition, a new binary endpoint '5-7 days without topical treatment use' will be introduced. This new endpoint will be evaluated by week and by treatment group as described for the primary analysis of the primary estimand ('composite') for the primary efficacy endpoints.

Scoring of PROs

POEM	Scored according to: https://www.nottingham.ac.uk/research/groups/cebd/documents/methodological-resources/poem-for-self-completion.pdf
DLQI	Scored according to: http://sites.cardiff.ac.uk/dermatology/quality-of-life/dermatology-quality-of-life-index-dlqi/dlqi-instructions-for-use-and-scoring/

Trial ID: LP0162-1343	Date: 15-Jun-2021	Version: 1.0 Page 13 of 22
-----------------------	-------------------	-------------------------------

6.6.5 Exploratory analyses

Reduction of Worst Daily Pruritus NRS (weekly average) of at least 4 from baseline to each scheduled assessment up to Week 15 will be based on subjects in the FAS with a baseline Pruritus NRS weekly average of at least 4.

Change from baseline in EASI score

In addition to the repeated measurements analysis of percentage reduction from baseline in EASI score, which was planned in the protocol, the same analysis will be conducted for the absolute change from baseline in EASI scores.

Subgroup analyses

To assess the consistency of the number of responders for the primary composite estimand across subgroups, IGA 0/1 and EASI75 will be presented descriptively by baseline IGA.

6.6.6 AxMP (TCS) accountability

For each subject, the weight of TCS used for a given visit interval (WGTUSED) will be calculated as the difference between the weight of the tubes dispensed (WGTDISP) and the weight of the returned tubes (WGTRET):

- if $WGTRET \leq WGTDISP$ then $WGTUSED = WGTDISP - WGTRET$
- if $WGTRET > WGTDISP$ then $WGTUSED = 0$.

All tubes dispensed at a visit are assumed to be returned at the subsequent visit where new tubes are dispensed. The amount of TCS used from these tubes will be attributed to the period between these two visits.

When tubes are not returned as specified in the protocol, the following rules will be applied:

- If a dispensed tube is not returned at all and the subject remains in the study, two different approaches will be applied to explore two extreme assumptions:
 1. It will be assumed that the missing tube has been fully used by the subject in the period between the date the tube was dispensed, and the date of the next subsequent visit attended by the subject. Estimated content (100 g) for the kit number will be used as a contribution to the WGTRET.

Trial ID: LP0162-1343	Date: 15-Jun-2021	Version: 1.0 Page 14 of 22
-----------------------	-------------------	-------------------------------

2. It will be assumed that the missing tube has not been used at all by the subject in the period between the date the tube was dispensed, and the date of the next subsequent visit attended by the subject, i.e. contribution from the tube to the WGTRET is set to 0.

- In the case where tubes from the last dispensing visit are not returned due to the subject being withdrawn from the trial, the amount of TCS used from these tubes will not be calculated (i.e. set to missing).

If a subject does not attend a planned visit, daily usage (DAYUSE) is calculated for the period between the tubes being dispensed and the subsequent dispensing visit, i.e.

$DAYUSE = WGTUSED / DURATION$ where $DURATION = ENDDATE$ (date of the subsequent dispensing visit)- $STARTDATE$ (date of the tubes being dispensed). The amount of TCS used for each visit in the period (missing visit(s) and the first visit after the tubes being dispensed) is calculated by multiplying daily usage (DAYUSE) by the number of days between the visit and the previous visit. For missing visits, the planned dates according to the trial schedule will be used.

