9.8.1.2 Labelling and packaging of AxMP (TCS)

The AxMP will be packaged in individually numbered kits that contain tubes of TCS cream with a total weight of approximately 180-225 g.

Primary and secondary packaging materials (tube and outer kit carton, respectively) will be individually labelled.

The labelling of AxMP will be in accordance with Annex 13 ([25](#)), local regulations, and trial requirements. Label text will be translated into local languages, as required.

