14.3.9 Analysis of other endpoints

The binary other endpoints, reduction from baseline to Week 16 of DLQI ≥ 4 points among subjects with baseline DLQI ≥ 4 and reduction from baseline to Week 16 of POEM score ≥ 4 points in subjects with baseline POEM score ≥ 4 , will be summarised by treatment group.

To evaluate the efficacy related to health care resource utilisation, the amount of TCS used (assessed as the amount of TCS used between visits), and the cumulative amount of TCS used will be determined by 2-week periods. The amount of TCS used and the cumulative amount of TCS used will each be logarithm-transformed prior to analysis. Due to potential zero valued ‘amount of TCS used’, 1 will be added to the values prior to transformation. This transformation has in a similar trial proven the model below to fit data better compared to leaving the data untransformed. Data will be analysed by a repeated measurements model with an unstructured covariance matrix and the mean modelled as follows:

$$\text{Log}(Y+1) = \text{treatment} \times \text{visit} + \text{baseline IGA}$$

where ‘Y’ is either the amount of TCS used or the cumulative amount of TCS used. Data obtained after permanent discontinuation of IMP or after initiation of rescue treatment will be excluded from the analyses.

The estimated parameters will be transformed back to the original scale using the exponential function, thus producing estimated geometric means and estimated ratio of means which will be presented together with 95% CIs.

Results obtained after initiation of rescue treatment will be excluded from the analyses.

In addition, TCS use (AxMP) <5 g at Week 16 will be analysed according to the primary analysis of the primary estimand for the primary endpoint.

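### The SAP's two rules for unreturned TCS tubes compute the reverse of the assumptions they state

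*SAP*

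**What the plan says.** SAP 6.6.6 defines the weight used in a visit interval (WGTUSED) as the "difference between the weight of the tubes dispensed (WGTDISP) and the weight of the returned tubes (WGTRET"), set to 0 if the returned weight exceeds the dispensed weight.

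When a tube is never returned and the subject stays in the study, two extreme assumptions are applied:

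- Rule 1, the missing tube was fully used: "Estimated content (100 g) for the kit number will be used as a contribution to the WGTRET".
- Rule 2, the missing tube was not used at all: "contribution from the tube to the WGTRET is set to 0".

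SAP 6.6.4 (Amount of TCS used) assigns the roles: "The primary analysis will be using the most conservative assumption that all missing tubes were fully used". The no-use assumption is the sensitivity analysis.

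Protocol 9.8.1.2 describes the supply as "individually numbered kits that contain tubes of TCS cream with a total weight of approximately 180-225 g". Neither document gives the tube size or the number of tubes per kit. Protocol 14.3.9 sets the analysis scale: "The amount of TCS used and the cumulative amount of TCS used will each be logarithm-transformed prior to analysis", after adding 1 to each value. It also says that "TCS use (AxMP) <5 g at Week 16 will be analysed according to the primary analysis of the primary estimand", without a rule for lost tubes.

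**The concern.** WGTRET is the weight that came back, and it is subtracted. Crediting 100 g to it treats the lost tube as returned full, which is the no-use assumption. Crediting 0 treats all its contents as gone, which is the full-use assumption. The operations attached to the two rules are therefore the wrong way round. Either the contributions were swapped or WGTRET was written where WGTUSED was meant; the SAP does not say which.

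A second ambiguity sits in the same sentence. The rules are worded per tube, but the 100 g is given for the kit number, while a kit totals about 180-225 g.

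At stake are the amount and cumulative amount of TCS used, which Protocol 14.3.9 analyses as the evidence on health care resource utilisation. The analysis described as primary and most conservative would show the lower use.

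**Working it through.** **Inputs.** The definition of WGTUSED, the zero floor, the two rules and the 100 g come from SAP 6.6.6. The primary and sensitivity roles come from SAP 6.6.4. The kit weight of 180-225 g is from Protocol 9.8.1.2, the log(Y+1) scale from Protocol 14.3.9, and 50 subjects per arm from about 100 randomised 1:1 (Protocol 14.1). Tube sizes, the use from other tubes and the number of lost tubes are my assumptions, since the documents give none of them.

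**Formulas.** Let D be the dispensed weight, t the weight of the lost tube, u the use from the other tubes, and R the weight of the tubes that came back, so R = D - t - u.

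- Rule 1 as written: max(D - R - 100, 0) = max(t + u - 100, 0). Its assumption requires t + u.
- Rule 2 as written: D - R = t + u. Its assumption requires u.

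**Results with u = 20 g and one lost tube.** Tube sizes are chosen so that whole tubes total 180-225 g.

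| t (g) | Rule 1 as written | Rule 1 as meant | Rule 2 as written | Rule 2 as meant |
|---|---|---|---|---|
| 45 | 0 | 65 | 65 | 20 |
| 90 | 10 | 110 | 110 | 20 |
| 100 | 20 | 120 | 120 | 20 |
| 112.5 | 32.5 | 132.5 | 132.5 | 20 |

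Rule 1 as written gives less use than rule 2 in every row. The two results are exchanged exactly only at t = 100 g. At other sizes the fixed 100 g adds a further error: at 45 g, rule 1 falls below even the 20 g of the no-use assumption.

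**Does another reading of WGTDISP rescue the rules?** Suppose the lost tube is left out of the dispensed weight, although it was dispensed. Rule 2 then gives u, which is right. Rule 1 gives max(u - 100, 0), which is 0 g at u = 20 g where 120 g is meant for a 100 g tube. The primary rule is wrong either way.

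**Do the possible repairs agree?** Reading WGTUSED for WGTRET, leaving the lost tube out of the subtraction and keeping the fixed 100 g makes rule 1 equal to u + 100. Swapping the contributions makes it u + t. At u = 20 g and t = 100 g both give 120 g; at t = 45 g they give 120 g and 65 g. They agree only if the tube holds 100 g.

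**Size on the analysis scale, t = 100 g, one interval.** The shift in one subject's log value is:

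- u = 0: ln(101) - ln(1) = 4.615. Divided by 50 this is 0.0923, a factor of exp(-0.0923) = 0.912.
- u = 20: ln(121) - ln(21) = 1.751. Divided by 50 this is 0.0350, a factor of 0.966.

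One affected subject thus lowers that arm's geometric mean of Y+1 by about 3.4% (u = 20) to 8.8% (u = 0). Three affected subjects give factors of 0.900 and 0.758, so about 10% to 24%. These are simple arm means of the logs, without model adjustment.

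**Size for the cumulative amount.** With 20 g in each of the eight two-week periods (160 g) and one lost 100 g tube, the shift is ln(261) - ln(161) = 0.483. Divided by 50 this is 0.0097, about 1.0%; for three subjects, about 2.9%.

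**The <5 g endpoint, if rule 1 were applied to it.** Take two 100 g tubes, one lost, and 2 g used from the other: D = 200, R = 98. As written, 200 - 98 - 100 = 2 g, which meets the criterion. As meant, 102 g, which does not.

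**The case against.** The strongest reply is that the intent is plain. SAP 6.6.6 states both assumptions in words, SAP 6.6.4 repeats them and names the primary one, and a careful programmer would follow the words. If the formula were followed instead, the outputs would show less cream under full use than under no use, which is impossible on its face. Both analyses and both histograms are planned, so the slip could be noticed. This limits the likely harm. It does not remove the error: the SAP describes itself as the more technical elaboration of the protocol, and its formula contradicts its text.

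It can also be said that 100 g is most naturally a tube weight, since two such tubes make 200 g, inside the kit range. That is plausible, and the 45, 90 and 112.5 g rows are hypothetical. But the sentence ties the figure to the kit number, so the point needs a statement. The reversal itself does not depend on it.

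The percentages for one interval are the larger ones, and the cumulative effect is much smaller, as shown above. The scope is also narrow. Tubes from the last dispensing visit that are unreturned because of withdrawal are set to missing, and data after rescue treatment or permanent discontinuation of IMP are excluded from the models. These limits stand.

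On the <5 g endpoint, one may argue that it inherits the primary assumption from the amount of TCS. No text says so; this is a gap in detail rather than a shown error.

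**Conclusion.** The concern holds. As written, both rules in SAP 6.6.6 yield the reverse of what they state, and nothing elsewhere in the SAP or protocol corrects them. For each lost tube, rule 1 is too low by 100 g, or by the whole interval's use if that is under 100 g. Rule 2 is too high by the lost tube's dispensed weight. If the SAP is programmed literally and tubes hold 100 g, the primary and sensitivity results carry each other's labels.

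The effect on the comparison between arms cannot be given, because it depends on how many tubes are lost in each arm. The endpoints concerned are in the category of other endpoints and are not formally tested. IGA 0/1, EASI75 and the key secondary endpoints are untouched. This should be fixed, but it does not threaten the trial's main conclusions.

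**What to change.** In SAP 6.6.6, adopt one of two corrections, which are equivalent once the tube's own weight is used:

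- Keep the contributions on WGTRET and swap them. A fully used tube contributes 0 (or the empty-tube weight if weights are gross), and an unused tube contributes its full dispensed weight.
- Define the contributions on WGTUSED. A fully used tube contributes its content and an unused tube contributes 0, with the lost tube left out of the subtraction.

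In either case, replace the fixed 100 g for the kit number with the dispensed weight or content of the missing tube, and state the tube size and the number of tubes per kit. Add one sentence to SAP 6.6.4 naming the rule that the <5 g endpoint at Week 16 uses.

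The cost is a few words in 6.6.6 and that one sentence. No new data are needed.

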6.7 Analysis of Safety

As specified in the protocol, the analysis of safety will be based on the safety analysis set and the safety follow-up analysis set.

6.7.1 Adverse events

Adverse Events will be summarised and listed. The summaries will be split into the treatment period and the safety follow-up period. Adverse Events occurring prior to the first dose will only be listed.

Assignment of AEs to periods

An Adverse Event (AE) will be assigned to a given period (treatment period or safety follow-up) if the start date is after the start date and before the end date of that period (see Section [6.8.2, Table 4](#)).

For AEs with start day on the same day as the first dose was given, only AEs starting after the first dose was given will be considered treatment-emergent and assigned to the treatment period.

AEs starting on the day of exposure end (as defined in Section [6.8.2](#)) will be assigned to the treatment period.

Trial ID: LP0162-1343	Date: 15-Jun-2021	Version: 1.0 Page 15 of 22
-----------------------	-------------------	-------------------------------

For handling of incomplete start dates of AEs, see Section [6.8.3](#).

Sort order of AE tables

Generally, AE tables by system organ class and/or preferred term will primarily be sorted alphabetically by SOC, and the preferred terms within the SOC will be sorted by decreasing number of events found in any of the treatment groups. The treatment group itself will not be considered in the sorting.

Other adverse events of interest

A MedDRA search on all reported AEs will be made to capture AEs belonging to injection site reactions. The MedDRA search to capture this safety area of interest was performed using the following high-level terms (based on primary and secondary terms): ‘administration site reactions NEC’, ‘application and instillation site reactions’, and ‘injection site reactions’. As only primary terms are available in SDTM data, a list of preferred terms included within the high-level terms are used to account for secondary terms. The list has been reviewed prior to unblinding of the trial.

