	
The trial consists of a screening period (Week -6/-2 to Week 0), a treatment period (Week 0 to Week 16), and a safety follow-up period (Week 16 to Week 20).
 
The screening period has a minimum duration of 2 weeks and a maximum duration of 6 weeks. The exact duration of the screening period depends on the length of required washout of AD treatment as defined by the exclusion criteria. If no washout is required or if only a 2-week washout period is required, the screening period is reduced to 2 weeks and only 1 screening visit at Week -2 is required.
 
Following the screening period, eligible subjects will be randomised at baseline (Week 0) to treatment with either tralokinumab or placebo and initiate administration of the investigational medicinal product (IMP). The IMP will be administered every second week during the treatment period, and the last IMP administration (relating to this protocol) will occur at Week 14.
 
Subjects in both treatment groups will also receive an AxMP, i.e. TCS. At baseline (Week 0), the subjects will be allowed to initiate treatment once daily with the supplied TCS on areas with active lesions of AD and continue this treatment, as needed, throughout the treatment period. The TCS use will be monitored throughout the trial.
 
All subjects must use an emollient twice daily (or more, as needed) for at least 14 days prior to randomisation and will continue this background treatment throughout the trial (including the safety follow-up). On lesional skin, emollients should only be applied at a time when TCS is not applied; on TCS-untreated areas, the emollients may be applied at all times.
 
Subjects who during the treatment period or safety follow-up experience intolerable AD symptoms can be treated with rescue treatment according to investigators discretion and will thus not be deprived from effective therapy.
 
Subjects who complete the 16-week treatment period (relating to this protocol) may enter a long-term extension trial (ECZTEND). All subjects completing the treatment period, except for those who enter the long-term extension trial, will have safety follow-up assessments 6 weeks after last IMP administration.
 
The primary and secondary endpoints will be assessed at Week 16, and the final safety assessments will be conducted at Week 20.

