During the initial treatment period in the AD pool, the frequency of serious adverse events (SAEs) was lower for tralokinumab (2.1%) than for placebo (2.8%). The majority of SAEs in both treatment groups were severe events, with similar frequencies for tralokinumab (1.5%) and placebo (1.7%). The frequencies of SAEs leading to permanent discontinuation of IMP were low and similar for tralokinumab (0.6%) and placebo (0.8%). The outcome of the majority of SAEs were recovered/resolved for both tralokinumab (32 of 38 events) and placebo (16 of 22 events).

During prolonged treatment with tralokinumab with or without TCS from 16 up to 52 weeks, the safety profile was consistent with the initial 16-week treatment period based on overall frequencies of AEs, SAEs, severe AEs, and AEs leading to permanent discontinuation of IMP as well as the patterns of event types within each of these AE categories.

Tralokinumab-treated subjects had a greater mean initial increase from baseline in eosinophil count compared with subjects treated with placebo. However, the increase in the tralokinumab-treated subjects was transient, and mean eosinophil counts returned to baseline

during continued treatment. No other clinically significant biochemistry parameters were identified from the completed phase 3 trials.

Data from the trials with tralokinumab in AD showed that the incidence rate of ADA and neutralising antibodies after 16 weeks of treatment was low and similar for tralokinumab and placebo, confirming the low immunogenicity of tralokinumab.

Overall, there were no indications that treatment with tralokinumab was associated with a higher risk of the following safety areas: skin infections requiring systemic treatment, eczema herpeticum, severe and serious infections (including any clinical endoparasitosis, opportunistic infections, and tuberculous infections), malignancies, anaphylaxis, serious allergic reactions, and immune complex disease. However, AEs of conjunctivitis, keratitis, and injection site reactions were more frequent with tralokinumab than placebo.

Thus, tralokinumab has a favourable safety profile, without any important risks identified in the clinical trials conducted to date.

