lesional skin, emollients should only be applied at a time when TCS is not applied; on TCS-untreated areas, the emollients may be applied at all times. The emollient treatment is further described in Section 9.4.

Eligibility will be assessed both at the (first) screening visit and prior to randomisation at baseline (Week 0; Visit 3) as described in Section 8.

Treatment period (Week 0 to Week 16)

Following the screening period, eligible subjects will be randomly assigned to one of the following treatment groups:

- Tralokinumab 600 mg (4 mL) at baseline, then 300 mg (2 mL) Q2W + TCS.
- Placebo (4 mL) at baseline, then placebo (2 mL) Q2W + TCS.

The IMPs, tralokinumab and placebo, are described in Section 9.1.1 and the treatment assignment is described in Section 9.3. The IMP will be administered by subcutaneous (SC) injections every second week throughout the treatment period as described in Section 9.2. The last dose of IMP will be administered at Week 14.

Subjects in both treatment groups will also be supplied with an AxMP, i.e. a TCS cream (mometasone furoate) as described in Section 9.1.2. The subjects will apply a thin film of the supplied TCS once daily on areas with active lesions as needed and as described in Section 9.2.2. Lower potency TCS or TCI may be prescribed if needed on body areas where the supplied TCS is not advisable or on areas where continued treatment with TCS is considered unsafe. Topical therapy should be discontinued when control is achieved; discontinuation should preferably be gradual. The safety and appropriateness of continued or repeated courses of TCS therapy will be monitored and supervised by the site staff.

Subjects who during the treatment period or safety follow-up experience intolerable AD symptoms can be treated with rescue treatment according to investigators discretion as described in Section 9.5.

Subjects, who complete the 16-week treatment period, may be invited to enter a long-term extension trial conducted under a separate protocol (ECZTEND).

Safety follow-up period (Week 16 to Week 20)

After the treatment period, all subjects who do not enter the long-term extension trial will complete an off-treatment follow-up period for assessment of safety, PK, and ADA.

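### The SAP's grouped count of injection site reactions can include reactions to the study cream, because its search takes in application-site terms and states no rule to remove them

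*SAP*

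**What the plan says.** SAP 6.7.1, under other adverse events of interest, announces the search: "A MedDRA search on all reported AEs will be made to capture AEs belonging to injection site reactions". Three high-level terms define it: *administration site reactions NEC*, "application and instillation site reactions", and *injection site reactions*. Because the study data hold only primary terms, "a list of preferred terms included within the high-level terms are used to account for secondary terms". The one safeguard mentioned is "The list has been reviewed prior to unblinding of the trial". The list is not reproduced, and no criterion for keeping or dropping a term is given.

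Protocol 7.1 and 9.2.1 give the IMP by subcutaneous injection only. On the cream, the protocol synopsis says: "Subjects in both treatment groups will also receive an AxMP, i.e. TCS". Protocol 7.1 adds: "The subjects will apply a thin film of the supplied TCS once daily on areas with active lesions as needed". Emollient is mandatory for all subjects (Protocol 9.4), and lower-potency topical steroids or calcineurin inhibitors are allowed on some areas (Protocol 9.2.2).

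Protocol 5.2 reports from earlier trials that "AEs of conjunctivitis, keratitis, and injection site reactions were more frequent with tralokinumab than placebo". Injection site reactions are not among the six adverse events of special interest in Protocol Panel 10.

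**The concern.** The category is named for a reaction to an injected product, but one of its three components describes reactions to applied products. In this trial the products applied to skin are the study cream, other permitted topicals and emollient. An event at a cream site that is coded to an application-site term meets the search definition as written, and so could one coded to a general administration-site term.

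At stake is how the grouped result for a recognised local effect of tralokinumab is read. This search is the only grouped analysis of injection site reactions that either document describes. Because these reactions are not on the special-interest list, no extra eCRF data are collected that would sort such events afterwards.

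**Working it through.** **Step 1: is there a figure to reproduce?** No. The documents give no rate for injection site reactions in either arm and none for cream reactions. Protocol 14.1 gives about 100 subjects randomised 1:1, so about 50 per arm. Protocol 14.3.5 plans no formal testing, only 95% CIs. All rates below are assumptions that show direction and scale.

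**Step 2: formula.** Let p be the probability of a true injection site reaction and q the probability of a cream reaction coded to a searched term, assumed independent. The probability of being counted in an arm is 1 − (1 − p)(1 − q). If q is the same in both arms, the difference in counted rates is (1 − q)(pT − pC), so it shrinks only by the factor 1 − q. The ratio moves towards 1, because both rates rise and the smaller one rises proportionally more.

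**Step 3: numbers, assuming pT = 10% and pC = 2%, n = 50 per arm.** Example for q = 5% in both arms: tralokinumab 1 − 0.90 × 0.95 = 14.5%; placebo 1 − 0.98 × 0.95 = 6.9%; difference 7.6 points; ratio 2.1. The half-width is 1.96 × √(a(1 − a)/50 + b(1 − b)/50), with a and b the counted rates. This Wald form is rough at such low counts and serves only to compare widths.

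| Cream reactions, tralokinumab / placebo | Counted rates | Difference (points) | Ratio | 95% CI half-width (points) |
|---|---|---|---|---|
| none | 10.0% / 2.0% | 8.0 | 5.0 | 9.2 |
| 2% / 2% | 11.8% / 4.0% | 7.8 | 3.0 | 10.4 |
| 5% / 5% | 14.5% / 6.9% | 7.6 | 2.1 | 12.0 |
| 10% / 10% | 19.0% / 11.8% | 7.2 | 1.6 | 14.1 |
| 2% / 5% | 11.8% / 6.9% | 4.9 | 1.7 | 11.4 |
| 5% / 10% | 14.5% / 11.8% | 2.7 | 1.2 | 13.2 |
| 10% / 5% | 19.0% / 6.9% | 12.1 | 2.8 | 12.9 |

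The last row reverses the imbalance: 1 − 0.90 × 0.90 = 19.0% and 1 − 0.98 × 0.95 = 6.9%.

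**Step 4: a second assumed pair, 7% versus 1%.** With no cream reactions the difference is 6.0 points and the ratio 7.0. Equal cream rates of 2%, 5% and 10% give differences of 5.9, 5.7 and 5.4 points and ratios of 3.0, 2.0 and 1.5. The pattern is the same.

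**Step 5: reading.** With equal cream rates the absolute difference barely changes, while the ratio falls and the interval widens. With unequal rates the absolute difference can move materially in either direction, depending on which arm has more cream reactions.

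**The case against.** Several counter-arguments are sound and set the size of this point.

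- *Miscounting is conditional.* It needs a cream reaction to be coded to an application- or administration-site term. Protocol 13.3 asks for a specific diagnosis where possible and gives allergic contact dermatitis as an example; events coded to ordinary skin terms are not captured. Exclusion criterion 1 also removes subjects for whom topical steroids are inadvisable, including for intolerance or hypersensitivity. A reader might infer that cream reactions will be counted as injection reactions. The documents support only that they can be.
- *Other tables separate the terms.* Protocol 14.3.12.1 tabulates events by preferred term within system organ class, and tabulates relationship to IMP and to the cream separately. This stands. It does not correct the grouped count, but a careful reader can take that count apart.
- *The list was reviewed before unblinding and cannot be seen.* Cream-related terms may already be out. The SAP does not say so, and gives no criterion by which they would be.
- *A broad search is defensible.* It catches injection events reported in other words; Protocol 14.3.3 itself speaks of application of IMP. That justifies keeping the broad set, but not as the only grouped definition.
- *Filtering on causality would be worse.* It would put investigator judgement into the event definition. This is right, and the remedy below is defined by term only.

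A reader might also infer that the search understates tralokinumab's local risk because placebo subjects use more cream. Cream use is as needed, and its amount is an endpoint still to be measured (Protocol Panel 3). Neither document gives cream use or cream-reaction rates by arm, so that direction is not established. Nor is this the only pre-defined safety topic, since the protocol lists six events of special interest.

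**Conclusion.** The point holds as a limited one. As written, the SAP's injection site reaction category admits application-site events in a trial where the IMP is only injected and both arms are supplied with a cream, with no stated exclusion. Under the assumed 10% versus 2%, equal cream rates of 2% to 10% take the ratio from 5.0 down to between 3.0 and 1.6, with almost no change in the absolute difference. A material bias in the difference requires cream reactions to be unequal between arms. These sizes rest on assumed rates, on independence of the two kinds of reaction, and on cream events reaching the searched terms.

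The effect stops at this grouped category. The tables by preferred term and by relationship to the cream remain, the protocol's safety endpoints (number of treatment-emergent adverse events per subject, and treatment-emergent anti-drug antibodies) are unchanged, and no efficacy result is affected. Priority: low to moderate.

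**What to change.** Before unblinding, amend SAP 6.7.1 as follows.

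1. Define the main grouped table by the preferred terms under the high-level term *injection site reactions*, by term alone and without a causality filter.
2. Show the application and instillation site terms and the administration site NEC terms as separate rows, by arm, with recorded relationship to IMP and to the cream displayed. Under Protocol 13.3 relationship to the cream is assessed only for events judged not related to IMP, so mark it as not assessed for the others.
3. Keep the present three-term search as a supplementary total, for comparison with any broader search.
4. Attach the reviewed preferred-term list. If cream-related terms have already been removed from it, say so and give the criterion.

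The cost is a short SAP change and one extra table, with no new data. The downside is that the main category may miss an injection event coded to a non-injection term; the supplementary total would still show it if it falls under the other two high-level terms.
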